9.4 Treatment Accountability and Compliance

The unblinded pharmacist or other designated individual will maintain records of study treatment delivered to the study site, the inventory at the study site, the distribution to and use by each subject, and the return of materials to the Sponsor for storage or disposal. These records should include dates, quantities, batch/serial numbers, retest dates, in-clinic temperature log, and unique code numbers assigned to the product and study subjects.

Investigators will maintain records that adequately document that the subjects were administered the correct study treatment and reconcile the products received from the drug dispensing center. Investigational product will not be returned to the Sponsor until accountability has been fully monitored.

Administration of investigational product will be supervised by study site personnel to ensure compliance.

9.5 Prior and Concomitant Therapy

9.5.1 Prior and Concomitant Medications

Restricted prior therapies are provided in [Section 8.2](#).

All medications and other treatments taken by the subject during the study, including those treatments initiated before the start of the study, must be recorded on the eCRF.

Medications taken by or administered to the subject for the time period before Screening [REDACTED] will be recorded in the eCRF. After the dosing of investigational product, medication to treat minor treatment-emergent illness(es) is generally permitted. After 24 hours of completion of investigational product infusion, use of antiplatelet agent(s) will be at the discretion of the Investigator. After 24 hours, the following are allowed at the discretion of the Investigator: heparin, non-vitamin K antagonist oral anticoagulant such as dabigatran, rivaroxaban, apixaban, or other factor Xa inhibitors. Low dose heparin or low molecular weight heparin at a preventive dose are allowed from 24 hours after treatment completion and after no intracranial bleeding has been confirmed on 24 hours repeat brain imaging.

[figure not shown]
Any medication or therapy that is taken by or administered to the subject during the course of the study must be recorded in the eCRF. The entry must include the dose, regimen, route, indication, and dates of use.

10 STUDY PROCEDURES

Table 10-1 outlines the timing of procedures and assessments to be performed throughout the study. Section 12.6 specifies laboratory assessment samples to be obtained. See Sections 11 and 12 for additional details regarding efficacy assessments and safety assessments, respectively.

Table 10-1. Schedule of Assessments

This document is confidential.

This document is confidential.

Page 31 of 65

10.1 Informed Consent

Before performing any study-related procedures, the Investigator or designee will obtain the signed ICF from the subject or his/her legally acceptable representative.

In the event that rescreening occurs (see [Section 8.3](#)), the individual is required to sign a new ICF and must be assigned a new Subject Number.

10.2 Study Procedures

Assessments and corresponding timings are to be performed as outlined in the Schedule of Assessments ([Table 10-1](#)). [Section 12.6](#) specifies laboratory assessment samples to be obtained.

[REDACTED]

Efficacy assessments are described in [Section 11](#). Efficacy endpoints include occurrences of recurrent stroke, neurological and functional outcomes (via NIHSS and mRS [REDACTED]).

[REDACTED]

Safety assessments are described in [Section 12](#) and include bleeding assessment (occurrences of sICH and asymptomatic ICH), vital signs, physical and neurological examinations, ECGs, laboratory assessments, and AEs.

[REDACTED]

The Investigator may, at his/her discretion, arrange for a subject to have an unscheduled assessment, especially in the case of AEs that require follow-up or are considered by the Investigator to be possibly related to the use of investigational product. The unscheduled visit page in the eCRF must be completed.

Study discontinuation procedures are described in [Section 8.4](#).

Assessments will be done at each visit as detailed in the subsections below.

[REDACTED] [REDACTED]

[REDACTED] [REDACTED]
[REDACTED] [REDACTED]
[REDACTED] [REDACTED]
[REDACTED] [REDACTED]
[REDACTED] [REDACTED]
[REDACTED] [REDACTED]
[REDACTED] [REDACTED]

This document is confidential

The page is heavily redacted with black bars and a large black rectangle. The redacted content includes the company name, document identifier, and the majority of the page text.

This document is confidential.

Page 35 of 65

This document is confidential

11 EFFICACY ASSESSMENTS

The Schedule of Assessments ([Table 10-1](#)) outlines the efficacy assessments to be performed throughout the study and their timing. Efficacy endpoints include occurrences of recurrent stroke, neurological and functional outcomes (via NIHSS and mRS assessments) [REDACTED]

[figure not shown]
11.1 National Institute of Health and Stroke Scale

The NIHSS is a systematic assessment tool that provides a quantitative measure of stroke-related neurologic deficit. It consists of 11 items, each with a score range of 0 to 2-4, with higher scores indicating more deficit/impairment in that specific ability. The total score ranges from 0 (no deficit) to 42 (dead). The score and corresponding description for the NIHSS is provided in [Appendix 2](#).

[figure not shown]

11.2 Modified Rankin Scale

The mRS measures the degree of disability or dependence in the daily activities of patients who have suffered a stroke. The scale runs from 0 (perfect health without symptoms) to 6 (dead).

and corresponding description is provided in [Appendix 3](#).

12 SAFETY ASSESSMENTS

Safety assessments (bleeding assessment, vital signs, physical and neurological examinations, ECGs, laboratory assessments, and AEs) are to be performed at protocol-specified visits, as specified in the Schedule of Assessments ([Table 10-1](#)).

12.1 Bleeding Assessment

Bleeding assessment will be done by the Investigator or designee and categorized as sICH and asymptomatic ICH. The occurrence of sICH and asymptomatic ICH within 36 hours and 7 days after dosing will be recorded.

12.2 Medical History

Medical history will be recorded at Screening [REDACTED]. Investigators should document the occurrence, signs, and symptoms of the subject's preexisting conditions, including all prior significant illnesses, up to and including 1 year before Screening [REDACTED]. Additional preexisting conditions present at the time when informed consent is given and up to the time of the initiation of dosing [REDACTED] are to be regarded as concomitant illnesses. Medical history will include alcohol consumption and smoking history, if applicable.

Illnesses first occurring or detected during the study and/or worsening of a concomitant illness during the study are to be documented as AEs on the eCRF in accordance with Section [12.7](#). All changes not present at Baseline or described in the past medical history and identified as clinically noteworthy must be recorded as AEs.

Additionally, demographic data will be collected for all subjects and include date of birth or age according to applicable regulations, gender, and race/ethnicity.

12.3 Vital Signs

Vital signs (body temperature, pulse rate, respiration rate, systolic blood pressure, and diastolic blood pressure) will be measured at the visits indicated in the Schedule of Assessments ([Table 10-1](#)). All vital signs will be measured after the subject has been resting in a supine position for at least 5 minutes. Blood pressure measurements are to be taken in the same arm for the duration of the study.

Vital signs measurements will be repeated if clinically significant or machine/equipment errors occur. Out-of-range body temperature, pulse rate, respiratory rate, or blood pressure

measurements will be repeated at the Investigator's or designee's discretion. Any confirmed, clinically significant vital sign measurements must be recorded as AEs.

Body weight (without shoes) will be recorded will be recorded at Screening [REDACTED] only. For subjects who cannot stand on a scale, bed weight measurement is allowed at the Investigator's or designee's discretion.

12.4 Physical and Neurological Examination

A complete physical examination [REDACTED]

[REDACTED] will be performed at Screening [REDACTED]. Physical examinations will be performed by a physician.

[REDACTED]

12.5 12-Lead Electrocardiograms

A 12-lead, resting ECG will be obtained at the visits indicated in the Schedule of Assessments ([Table 10-1](#)).

[figure not shown]
At Screening [REDACTED], the Investigator will examine the ECG traces for signs of cardiac disease that could exclude the subject from the study. An assessment of normal or abnormal will be recorded; if the ECG is considered abnormal, the abnormality will be documented on the eCRF. Electrocardiograms will be repeated if clinically significant abnormalities are observed or artifacts are present at the Investigator's or designee's discretion.

[REDACTED]

12.6 Laboratory Assessments

Laboratory assessment samples ([Table 12-1](#)) are to be obtained at designated visits as detailed in the Schedule of Assessments ([Table 10-1](#)).

Table 12-1. Laboratory Assessments

Blood samples will be analyzed at each site. All laboratory reports must be reviewed, signed, and dated by the Investigator or designee. A legible copy of all reports must be filed with both the subject's eCRF and medical record (source document) for that visit. Any laboratory test result considered by the Investigator or designee to be clinically significant should be considered an AE (clinically significant AEs include those that require an intervention). Clinically significant abnormal values occurring during the study will be followed up until repeat test results return to normal, stabilize, or are no longer clinically significant.

12.7 Adverse Events

12.7.1 Adverse Events

An AE is any symptom, physical sign, syndrome, or disease that either emerges during the study or, if present at Screening [REDACTED], worsens during the study, regardless of the suspected cause of the event. [REDACTED]

Changes

in these conditions and new symptoms, physical signs, syndromes, or diseases should be noted on the AE eCRF during the rest of the study. Clinically significant laboratory abnormalities should also be recorded as AEs. Surgical procedures that were planned before the subject enrolled in the study are not considered AEs if the conditions were known before study inclusion; the medical condition should be reported in the subject's medical history.

Treatment-emergent AEs (TEAEs) are defined as events with onset dates on or after the start of the investigational product.

Subjects will be instructed to report AEs at each study visit. All AEs are to be followed up until resolution or a stable clinical endpoint is reached.

Each AE is to be documented on the eCRF with reference to date of onset, duration, frequency, severity, relationship to investigational product, action taken with investigational product, treatment of event, and outcome. Furthermore, each AE is to be classified as being serious or nonserious. Changes in AEs and resolution dates are to be documented on the eCRF.

For the purposes of this study, the period of observation for collection of AEs extends from the time the subject gives informed consent until the last follow-up visit. Follow-up of the AE, even after the date of therapy discontinuation, is required if the AE persists until the event resolves or stabilizes at a level acceptable to the Investigator.

When changes in the intensity of an AE occur more frequently than once a day, the maximum intensity for the event should be noted. If the intensity category changes over a number of days, then those changes should be recorded separately (with distinct onset dates).

Specific guidelines for classifying AEs by intensity and relationship to investigational product are given in [Table 12-2](#) and [Table 12-3](#).

Table 12-2. Classification of Adverse Events by Intensity

MILD: An event that is easily tolerated by the subject, causing minimal discomfort, and not interfering with everyday activities.

MODERATE: An event that is sufficiently discomforting to interfere with normal everyday activities.

SEVERE: An event that prevents normal everyday activities.

Table 12-3. Classification of Adverse Events by Relationship to Investigational Product

UNRELATED: This category applies to those AEs that are clearly and incontrovertibly due to extraneous causes (disease, environment, etc).
UNLIKELY: This category applies to those AEs that are judged to be unrelated to the test drug/study procedure but for which no extraneous cause may be found. An AE may be considered unlikely to be related to investigational product /procedure if or when it meets 2 of the following criteria: (1) it does not follow a reasonable temporal sequence from administration of the test drug /study procedure; (2) it could readily have been produced by the subject's clinical state, environmental or toxic factors, or other modes of therapy administered to the subject; (3) it does not follow a known pattern of response to the test drug/study procedure; or (4) it does not reappear or worsen when the drug/study procedure is readministered.
POSSIBLY: This category applies to those AEs for which a connection with the test drug /study procedure administration appears unlikely but cannot be ruled out with certainty. An AE may be considered possibly related if or when it meets 2 of the following criteria: (1) it follows a reasonable temporal sequence from administration of the drug /study procedure; (2) it could not readily have been produced by the subject's clinical state, environmental or toxic factors, or other modes of therapy administered to the subject; or (3) it follows a known pattern of response to the test drug /study procedure.
PROBABLY: This category applies to those AEs that the Investigator feels with a high degree of certainty are related to the test drug /study procedure. An AE may be considered probably related if or when it meets 3 of the following criteria: (1) it follows a reasonable temporal sequence from administration of the drug /study procedure; (2) it could not be reasonably explained by the known characteristics of the subject's clinical state, environmental or toxic factors, or other modes of therapy administered to the subject; (3) it disappears or decreases on cessation or reduction in dose (note that there are exceptions when an AE does not disappear upon discontinuation of the drug, yet drug-relatedness clearly exists; for example, as in bone marrow depression, fixed drug eruptions, or tardive dyskinesia); or (4) it follows a known pattern of response to the test drug/study procedure.
DEFINITELY: This category applies to those AEs that the Investigator feels are incontrovertibly related to test drug/study procedure. An AE may be assigned an attribution of definitely related if or when it meets all of the following criteria: (1) it follows a reasonable temporal sequence from administration of the drug /study procedure; (2) it could not be reasonably explained by the known characteristics of the subject's clinical state, environmental or toxic factors, or other modes of therapy administered to the subject; (3) it disappears or decreases on cessation or reduction in dose and recurs with re-exposure to drug (if rechallenge occurs); and (4) it follows a known pattern of response to the test drug /study procedure.

Abbreviation: AE, adverse event.

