5.4 Study Rationale

Tissue plasminogen activator (alteplase) is the only approved drug treatment for stroke in the US and, per the labeling, must be administered within 3 hours of stroke symptom onset. The approved window of administration in some other countries is 4.5 hours of stroke symptom onset.

LT3001 is a novel chemical entity designed to have both thrombolytic and free radical scavenging activities, which were characterized in various in vitro and in vivo models. Its advantages over IV rtPA include: shorter infusion time, within 24 hours of stroke onset (as opposed to 3 hours), better recanalization rate, prevention of reperfusion injury by scavenging free radicals, no effect on bleeding time, no evidence of increase in intracranial hemorrhage (as seen with IV rtPA), and ease of use.

This Phase IIa, double-blind, single-dose, randomized, placebo-controlled study is to evaluate the safety, tolerability, and potential efficacy of LT3001 drug product in subjects/patients with AIS. The safety and potential efficacy outcomes from this Phase IIa study will guide the design of future studies in subjects/patients with AIS.

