12.7.4 Suspected Unexpected Serious Adverse Reactions

Adverse events that meet all of the following criteria will be classified as suspected unexpected serious adverse reactions (SUSARs) and reported to the appropriate regulatory authorities in accordance with applicable regulatory requirements for expedited reporting:

- serious
- unexpected (i.e., the event is not consistent with the safety information in the IB)
- there is at least a reasonable possibility that there is a causal relationship between the event and the study treatment

The Investigator will assess whether an event is causally related to study treatment. The Sponsor [REDACTED] will consider the Investigator's assessment and determine whether the event meets the criteria for being reportable as a 7-day or 15-day safety report. Suspected unexpected serious adverse reactions (SUSARs) that are fatal or life-threatening must be reported to the regulatory authorities and the independent ethics committee (IEC)/institutional review boards (IRBs) (where required) within 7 days after the Sponsor [REDACTED] has first knowledge of them, with a follow-up report submitted within a further 8 calendar days. Other SUSARs must be reported to the relevant regulatory authorities and the IEC/IRBs within 15 calendar days after the Sponsor [REDACTED] first has knowledge of them.

The Sponsor [REDACTED] is responsible for reporting SUSARs and any other events required to be reported in an expedited manner to the regulatory authorities and for informing Investigators of reportable events, in compliance with applicable regulatory requirements within specific timeframes. Investigators will notify the relevant IEC/IRBs of reportable events within the applicable timeframes.

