### **10.3. Adverse Events / Adverse Drug Reactions**

An AE is any symptom, physical sign, syndrome, or disease that either emerges during the study or, if present at Screening [REDACTED] worsens during the study, regardless of the suspected cause of the event.

Treatment-emergent AEs (TEAEs) are defined as events with onset dates on or after the start of the IP. AEs with missing onset dates will also be included as TEAEs.

AE will be coded with Medical Dictionary for Regulatory Activities (MedDRA) in place at the time of analysis and grouped by SOC and PT.

An SAE is any untoward medical occurrence, in the view of either the Investigator or Sponsor, that:

- results in death
- is life-threatening
- results in inpatient hospitalization or prolongation of existing hospitalization
- results in persistent or significant disability/incapacity, and/or
- is a congenital anomaly/birth defect

Other important medical events that may not be immediately life-threatening or result in death or hospitalization, based upon appropriate medical judgment, are considered SAEs if they are thought to jeopardize the subject and/or require medical or surgical intervention to prevent one of the outcomes defining an SAE.

All AEs will be included in data listings and listed by subject, along with information regarding onset, duration, relationship and severity to investigational product, action taken with investigational product, treatment of event, and outcome.

Drug-related AEs are defined as AEs with possible, probable, or definite relationship to study drug.

AEs are classified as mild, moderate and severe in intensity-

All AE summaries will be restricted to TEAEs only.

The number and percentage of subjects as well as number of events will be presented for TEAE summaries. For summaries by SOC, PT, and maximum intensity, a subject will be counted once at the highest intensity for which the event occurred at the SOC level and the highest intensity for each unique PT within that SOC level. Summaries by relationship to study drug will be handled similar to the summaries by intensity.

The following summaries will be provided.

This document is confidential.

- Overall summary of TEAEs by treatment group and overall
- TEAEs within 90 days by SOC and PT
- TEAEs within 90 days by SOC, PT and maximum intensity
- TEAEs within 90 days by SOC, PT and maximum relationship to study drug
- Drug-related TEAEs within 90 days by SOC and PT
- Serious TEAEs by SOC and PT

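### The counted criteria in Table 12-3 conflict with their own category descriptions, and they steer an early post-infusion bleed toward Unlikely and out of the drug-related table

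*Protocol*

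**What the plan says.** Protocol 12.7.1 refers investigators to Table 12-3 to classify relationship to the investigational product. Each category has a short description followed by criteria to be counted.

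- **Possibly.** The connection "appears unlikely but cannot be ruled out with certainty". The count: "An AE may be considered possibly related if or when it meets 2 of the following criteria". The three are reasonable timing, that "it could not readily have been produced by the subject's clinical state, environmental or toxic factors" (or other treatment), and a known pattern of response to the test drug.
- **Unlikely.** Described as events judged unrelated for which no outside cause can be identified. The count is 2 of 4: timing does not fit, the clinical state or other treatment could readily have produced the event, there is no known drug pattern, and "it does not reappear or worsen when the drug/study procedure is readministered".
- **Probably.** 3 of 4: timing, no reasonable alternative explanation, improvement on stopping or reducing the dose (with a written exception), and a known pattern.
- **Definitely.** All four, where the third is "it disappears or decreases on cessation or reduction in dose and recurs with re-exposure to drug (if rechallenge occurs").

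SAP 10.3 draws the line above Unlikely: "Drug-related AEs are defined as AEs with possible, probable, or definite relationship to study drug". It then tabulates drug-related TEAEs and TEAEs by maximum relationship. Protocol 12.7.4 uses a separate test for expedited reporting, that "there is at least a reasonable possibility that there is a causal relationship between the event and the study treatment", and does not say which Table 12-3 categories satisfy it.

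**The concern.** Two of the three Possibly criteria are hard to meet in this setting. Every subject has an acute stroke, so neurological worsening, hemorrhage or death can often be put down to the clinical state. Other treatment also counts as an explanation, and Protocol 9.5.1 allows antithrombotics from 24 hours, inside the 36-hour window of the primary endpoint. On known pattern, Protocol 5.2.2 reports 12 healthy subjects exposed, Protocol 7.2 calls this the first study in AIS, and Protocol 5.4 tells sites there is "no evidence of increase in intracranial hemorrhage (as seen with IV rtPA"). That leaves timing.

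At stake are the drug-related and relationship tables in SAP 10.3, and possibly the investigator's input to the SUSAR judgement. The trial is small. With 24 subjects randomized 2:1 and all dosed, the LT3001 arm has 24 × 2/3 = 16 subjects, so one bleed moved between categories changes that arm's drug-related incidence for the term by 1/16 = 6.25 percentage points.

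**Working it through.** The plan gives no figure on this point, so there is none to reproduce. The check scores the rules of Table 12-3 directly.

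**Inputs**, each a yes/no judgement (1/0):
- T: timing is reasonable
- C: the clinical state or other treatment could readily have produced the event
- K: the event fits a known pattern of the drug
- D: the event improves on stopping or dose reduction
- R: the readministration item of Unlikely is counted as met because the drug is never given again

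**Scores**
- Unlikely = (1 − T) + C + (1 − K) + R, needs 2
- Possibly = T + (1 − C) + K, needs 2
- Probably = T + (1 − C) + D + K, needs 3
- Definitely needs all four of its criteria

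The first three Unlikely criteria are in effect the negations of the three Possibly criteria, so with R = 0, Unlikely = 3 − Possibly.

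**Early post-infusion bleed or deterioration (T = 1)**

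| Judgement | Possibly | Unlikely, R = 0 | Unlikely, R = 1 |
|---|---|---|---|
| C = 1, K = 0 | 1 of 3, not met | 2 of 4, met | 3 of 4, met |
| C = 1, K = 1 | 2 of 3, met | 1 of 4, not met | 2 of 4, met |
| C = 0, K = 0 | 2 of 3, met | 1 of 4, not met | 2 of 4, met |

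In the first row, Probably = 1 + 0 + D + 0, which is 1 or 2 and short of 3. Definitely fails because two of its four criteria fail. Of these four categories, Unlikely is the only one met on a literal count. The result is the same with R = 0, so the readministration item does not produce it. The clinical-state and known-pattern criteria do.

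**Count against description, first row.** The Possibly description covers a weak connection that cannot be excluded, which fits an event with good timing and a competing explanation. The count rejects it. The Unlikely description is for events with no identifiable outside cause, but one of its criteria is met precisely when such a cause is at hand. The count accepts it.

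**Overlap.** With R = 1, Unlikely = 4 − Possibly. Both reach 2 only when Possibly is exactly 2. That happens in 3 ways (one of the three Possibly criteria fails), times 2 values of D, giving 6 of the 2^5 = 32 combinations. With R = 0 there is no overlap. The table does not say which category prevails. The 32 combinations are a count of rule outcomes, not a probability that a given event falls in the overlap.

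**The case against.** A reader might infer that an early bleed is forced to Unlikely and can never count as drug-related. The documents do not support that. The counted rules are permissive, the Possibly description fits such an event, and one different judgement (C = 0 or K = 1) gives Possibly. Either judgement is open. Protocol 5.4 describes LT3001 as thrombolytic by design, so an investigator may accept bleeding as a known pattern. Protocol 8.2 excludes subjects with acute intracranial hemorrhage on imaging, so a new bleed need not be readily attributed to the stroke. The investigator's brochure, where anticipated AEs are listed, is not available here.

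A reader might also infer that repeat-dosing language is the cause. It is not: the first row of the table is unchanged without the readministration item, the Probably criterion on stopping the drug carries a written exception, and re-exposure under Definitely is conditional. Stopping can occur, since the infusion is halted for an SAE (Protocol 7.1). What remains is one untestable item and the overlap it creates.

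Finally, a reader might infer that the safety signal would be hidden or that bleeds would escape expedited reporting. The sICH, asymptomatic ICH, mortality and NIHSS-worsening analyses carry no causality condition, and all TEAEs and serious TEAEs are tabulated by arm. Protocol 12.7.3 requires SAE reports whatever the investigator's view of causality. Protocol 12.7.4 states its own test without citing Table 12-3, and the sponsor decides reportability.

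These objections limit the point but do not remove it. The conflict between counts and descriptions stands, as does the missing link between the categories and the 12.7.4 test, under which the investigator still assesses causality first.

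**Conclusion.** The point holds as an internal inconsistency worth correcting. If the investigator judges that timing fits, that the stroke could readily explain the event, and that no LT3001 pattern is known, the literal count leads to Unlikely, and SAP 10.3 then leaves the event out of the drug-related TEAE table. Those judgements are assumptions. The protocol's text makes them natural but does not dictate them.

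The exposure is confined to the drug-related and relationship tables, and possibly the investigator's input to the SUSAR judgement. The primary endpoint and the between-arm safety comparisons stand as they are.

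**What to change.** Keep the graded scale and change the wording of Table 12-3 in four places:

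1. Delete the readministration item from Unlikely.
2. State that a plausible explanation by the index stroke does not by itself make an event Unlikely when timing is reasonable and a drug contribution cannot be excluded.
3. State that the higher relationship category applies when two are met.
4. State that Possibly and above correspond to reasonable possibility in Protocol 12.7.4, and add a sentence to SAP 10.3 so that the drug-related tables use the same standard.

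The cost is this wording and any matching eCRF completion guidance. Somewhat more AEs will be labelled related, in both blinded arms. Replacing the scale with a single yes/no field would be simpler but is debatable: the maximum-relationship table in SAP 10.3 and the closest-association rule in Protocol 14.3.2.6 both need the grades.
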